4.2 Withdrawal of Subjects From Study Treatment and/or the Study

The duration of the study is defined for each subject as the date signed written informed consent is provided through the last follow-up visit on Day 254.

4.2.1 Reasons for Withdrawal/Discontinuation

Subjects may withdraw or discontinue from the study at any time and for any reason without prejudice to their future medical care by the investigator or at the study center. Every effort should be made to keep subjects in the study. The reasons for subjects not completing the study will be recorded. A subject may be withdrawn from the study or study treatment (ie, no longer receive study vaccine) for any of the following reasons:

1. Failure to continue to meet the protocol inclusion or exclusion criteria.
2. Noncompliance with the protocol.
3. Serious or intolerable AE(s) that in the investigator's opinion requires withdrawal or discontinuation from the study.
4. The subject has laboratory safety results that reveal clinically significant hematological or biochemical changes from the baseline values.
5. The subject has symptoms or an intercurrent illness not consistent with the protocol requirements or that justify withdrawal or discontinuation.
6. The subject is lost to follow-up.
7. Other reasons (eg, development of contraindications of use of study drug, use of disallowed substances).
8. If pregnancy occurs further vaccination will be discontinued.
9. The subject withdraws consent or the investigator or ILiAD Biotechnologies decides to discontinue the subject's participation in the study.

The investigator will also withdraw a subject if ILiAD Biotechnologies terminates the study. Upon occurrence of a serious or intolerable AE, the investigator will confer with the sponsor. If a subject is discontinued because of an AE, the event will be followed until it is resolved. Any subject may withdraw his or her consent at any time.

4.2.2 Handling of Withdrawals

Subjects are free to withdraw from the study or study treatment at any time upon request. Subject participation in the study may be stopped at any time at the discretion of the investigator or at ILiAD Biotechnologies request.

Subjects who discontinue study treatment or active participation in the study will no longer receive study vaccination but will continue to be followed and are not considered withdrawn. When a subject withdraws from the study, the reason(s) for withdrawal shall be recorded by the investigator on the relevant page in the electronic case report form (eCRF).

All subjects who discontinue from study treatment prematurely will follow the same visit schedule as other subjects without further vaccination.

Whenever possible, all subjects who discontinue from the study prematurely will stay in the study for safety reasons and will follow the schedule of events (Table 13-1) if they have received vaccination. Subjects who fail to return for final assessments will be contacted by the clinical site in an attempt to have them comply with the protocol. A subject will not be considered lost to follow-up until every attempt to contact the subject has been made, at minimum 2 (documented) phone calls, followed by a registered letter. Every effort should be made to collect safety data on subjects through the end-of-study visit.

It is vital to obtain follow-up data on any subject withdrawn from the study or study vaccine (ie, no longer receiving study vaccination) because of an AE or serious AE (SAE). In every case, efforts must be made to undertake protocol-specified safety follow-up procedures.

4.2.3 Replacements

Subjects who withdraw, are withdrawn or terminated from this study, or are lost to follow-up after signing the ICF but before receipt of any study vaccine may be replaced. Subjects who receive the study vaccine and subsequently withdraw, are discontinued from receiving further vaccination, are terminated from the study, or are lost to follow-up will not be replaced.

5 Study Treatments

5.1 Method of Assigning Subjects to Treatment Groups

Subjects will be randomly assigned to 1 of 4 treatment arms, in a 2:2:1:1 ratio, as presented in Table 3-1. An interactive response technology will be used to administer the randomization schedule centrally. Biostatistics will generate the randomization schedule using SAS® software Version 9.3 or later (SAS Institute Inc, Cary, North Carolina) for the interactive response technology, which will link sequential subject randomization numbers to treatment codes. The randomization schedule will be created by the dedicated randomization team, stored in a separate project area, and will be blinded to the project team with the exception of the unblinded pharmacy staff who will manage vaccine logistics, preparation, and administration, but will not be involved in study-related assessments or have subject contact for data collection following study vaccine administration.

5.2 Treatments Administered

Subjects in Treatment Arm A (N = 100) will receive an intranasal application of 2×0.4 mL (0.4 mL per nostril containing half the dose 5×10^8 bacteria to give a total dose of 10^9 CFU) BPZE1 and an IM injection of 0.5 mL placebo (sterile normal saline) to the deltoid region on Day 1 and an intranasal application of 2×0.4 mL (0.4 mL per nostril containing half the dose 5×10^8 bacteria to give a total dose of 10^9 CFU) BPZE1 on Day 85. Note: the first 24 subjects will be assigned to the 10^7 CFU dose.

Subjects in Treatment Arm B (N = 100) will receive an intranasal application of 2×0.4 mL (0.4 mL per nostril containing half the dose 5×10^8 bacteria to give a total dose of 10^9 CFU) BPZE1 and an IM injection of 0.5 mL placebo (sterile normal saline) to the deltoid region on Day 1 and an intranasal application of 2×0.4 mL (0.4 mL per nostril) placebo (formulation buffer) on Day 85. Note: the first 24 subjects will be assigned to the 10^7 CFU dose.

Subjects in Treatment Arm C (N = 50) will receive an intranasal application of 2×0.4 mL (0.4 mL per nostril) placebo (formulation buffer) and an IM injection of 0.5 mL Boostrix (aP vaccine, manufactured by GlaxoSmithKline, Research Triangle Park, North Carolina) to the deltoid region on Day 1 and an intranasal application of 2×0.4 mL (0.4 mL per nostril containing half the dose 5×10^8 bacteria to give a total dose of 10^9 CFU) BPZE1 on Day 85. Note: the first 24 subjects will be assigned to the 10^7 CFU dose.

Subjects in Treatment Arm D (N = 50) will receive an intranasal application of 2×0.4 mL (0.4 mL per nostril) placebo (formulation buffer) and an IM injection of 0.5 mL Boostrix (aP vaccine), to the deltoid region on Day 1 and an intranasal application of 2×0.4 mL (0.4 mL per nostril) placebo (formulation buffer) on Day 85. Note: the first 24 subjects will be assigned to the 10^7 CFU dose.

The dose of BPZE1 active ingredient will be administered to the subject within 60 minutes of removal from the freezer. One milliliter of WFI will be used to reconstitute the 1 mL vial of lyophilized BPZE1, but only 0.8 mL of vaccine will be withdrawn for administration into both nostrils. Following reconstitution, the VaxINator will be attached to the syringe, and 0.4 mL volume will be administered to each nostril. In the case of placebo nasal vaccination, a similar volume of WFI will be reconstituted into a vial containing only lyophilized buffer, followed by 0.4 mL volume administered into each nostril with the vaccinator. The VaxINator provides a uniform, controlled delivery, which allows the vaccinator to accurately

deliver 0.4 mL of vaccine to the initial nostril and then administer the remaining 0.4 mL to the opposite nostril.

The study vaccine will be labeled according to manufacturer specifications and include the statement “Caution: New Drug – Limited by Federal Law to Investigational Use.”

5.3 Identity of Investigational Product

The BPZE1 investigational vaccine is for intranasal administration and is an off-white lyophilized cake that contains genetically modified, live *B. pertussis* strain BPZE1 bacteria in lyophilization buffer.

ILiAD Biotechnologies will provide the CRO with the investigational vaccine and lyophilized buffer and the CRO will ensure proper labelling and distribution to the clinical sites.

The following supplies will be used for vaccination in the study:

Product	Dosage and Route of Administration:
BPZE1	2 × 0.4 mL (0.4 mL per nostril containing half the dose 5×10^8 bacteria to give a total dose of 10^9 CFU) administered intranasally by syringe + VaxINator
aP (Boostrix vaccine; manufactured by GlaxoSmithKline)	0.5 mL administered by IM injection to the deltoid region as active control
Intranasal placebo	2 × 0.4 mL (0.4 mL per nostril) reconstituted lyophilized buffer administered intranasally by syringe + VaxINator
IM placebo	0.5 mL sterile normal saline USP administered by IM injection to the deltoid region

Abbreviations: aP, acellular pertussis; CFU, colony-forming units; IM, intramuscular; USP, United States Pharmacopeia.

The intranasal placebo consists of lyophilized buffer diluted with sterile WFI which, is the same constituents in the same quantities as the BPZE1 investigational vaccine, absent the attenuated *B. pertussis* cells. The IM placebo is sterile normal saline (eg, normal saline).

Each vaccination with BPZE1 or Boostrix will utilize a single vial/syringe of product for each single use (1:1 assignment from study drug accountability). See pharmacy manual for specifics on product preparation.

5.3.1 Study Drug Packaging and Storage

The primary packaging for BPZE1 is a sterile glass 2R DIN vial with a chlorobutyl lyophilization stopper. The vial closure system is a combination of the stopper and the aluminum cap. The vials are crimped directly after the lyophilization process using the automated Fill & Finish unit that filled the vials with 1.0 mL suspension. The intranasal placebo dose contains the lyophilized buffer (ie, the vaccine formulation without the BPZE1 attenuated bacteria) and packaged in similar fashion.

Sufficient supplies of 1 vial for each subject in the clinical trial will be provided, with approximately 30% spare vials, packaged in a box of 49 vials for the BPZE1 drug product and 41 vials per box for the placebo. The vials and the boxes will be labeled with the required information applicable to investigational vaccine or placebo product used in clinical trials. The boxes either contain the vaccine or the placebo (lyophilized buffer only).

The 18G (or larger) needles, WFI, and syringes capable of holding 1 mL WFI used to reconstitute the investigational vaccine or placebo (formulation buffer) vials will be stored separately from the investigational vaccine vials at ambient temperature.

Boostrix will be procured from commercial stock and supplied as either single dose vials or prefilled syringes containing a 0.5 mL suspension for injection. The IM placebo is sterile normal saline United States Pharmacopeia (from a commercial supplier) and is supplied in a similar fashion.

Vaccines and placebos must be stored in a secure area (eg, locked room or locked refrigerator), protected from light and moisture as required by manufacturer. Vaccine will be shipped from ILiAD's European contract manufacturing organization to the CRO's repository and distribution center and should be stored at -20°C or below prior to shipping to the clinical sites, where the vaccine will be stored at -10°C or below. Clinical sites will store the vaccine in order to maintain viability of BPZE1 prior to reconstitution with WFI. The exposure of reconstituted BPZE1 to room temperature prior to vaccination should not exceed

60 minutes. A detailed description regarding the storage, reconstitution, and handling the investigational vaccines will be in the Pharmacy Manual.

Boostrix should be stored at 2°C to 8°C.

5.3.2 Investigational Product Accountability

The investigator will maintain accurate records of receipt of all study vaccine and placebo vials, including dates of receipt. In addition, accurate records will be kept regarding when and how much study vaccine is dispensed and used by each subject in the study. Reasons for departure from the expected dispensing regimen must also be recorded. At the completion of the study, to satisfy regulatory requirements regarding drug accountability, all study vaccine will be reconciled and retained or destroyed according to applicable regulations. No study vaccine will be destroyed until authorized in writing by the sponsor.

5.3.3 Other Supplies

Other clinical supplies that will be provided to the clinical sites for distribution to subjects include subject diaries, a measuring tool for measuring injection site erythema and swelling, and a thermometer for measuring body temperature.

A single VaxINator kit (sterile pouch containing a VaxINator atomization devise, a 1-mL single-use syringe, and other accessories not used in this protocol) is provided for each intranasal vaccination. The VaxINator boxes will be labeled with the required information applicable to a medical device accessory, for clinical trial investigational use only. The VaxINator is manufactured by Teleflex Medical. Teleflex has DMF #025388 for the VaxINator. The VaxINator is a conical shape plastic component that Luer-locks onto a 1-mL syringe. The VaxINator atomizes the liquid vaccine as it exits the syringe. The conical shape forms a plug in the nostril and high applied-pressure atomizes the liquid into a fine mist.

Kits for serum immune collection, mucosal immune collection, PBMCs and mucosal pertussis culture will all be provided and in sufficient quantity to allow for each subject sample collection. Bar coding will be applied to allow for sample tracking at the time of collection and throughout storage, transport, and testing.

Adequate supplies for immunization of individuals including, 18G (or larger) needles for injection, syringes, normal saline, nasal vaccinators, and blinding tape will be supplied. The

WFI will be provided for reconstituting the investigational vaccine and placebo vials for nasal immunization and will be stored separately from the investigational vaccine vials, at ambient temperature in a secure area.

5.4 Overdose Management

An overdose is any dose of study treatment given to a subject or taken by a subject that exceeds the dose described in the protocol. Any overdose, with or without associated AEs, must be promptly reported to the CRO's pharmacovigilance reporting center. In case of any AEs associated with the overdose, these should be reported on relevant AE/SAE sections in the eCRF. Any overdose should be recorded as a protocol violation and promptly reported to the sponsor. No overdoses are expected as the vaccine and adjuvant will be administered by clinical staff.

5.4.1 Treatment of Overdose

Treatment of overdose would include supportive and symptomatic care, according to the standards of care at the site. The investigator should promptly notify the medical monitor about the overdose and seek his/her input on the medical management, as needed.

5.5 Blinding

This is an observer-blinded study. To maintain the blind, placebo vaccination via intranasal and IM routes will be included and unblinded pharmacy staff will manage vaccine logistic, preparation, and administration (when necessary) so as to maintain the blind from the remainder of the study personnel and subjects. The pharmacy staff will not be involved in study-related assessments or have subject contact for data collection following study vaccine administration.

The full database lock will occur on Day 113 and all data collected through Day 113 will be included in the CSR and submitted to regulatory authorities. A subsequent longer-term safety follow-up, including longer-term persistence of immune responses, will occur through Day 254. These data will be provided in an addendum to the CSR. The clinical site study team directly participating in subject contact/care will remain blinded to the treatment assignment during this extended safety follow-up period. All unblinded data analyses prior to full database lock on Day 113 will be handled by the unblinded team of statisticians and

programmers. A strict firewall between the blinded and unblinded teams will be maintained during study conduct.

5.5.1 Breaking the Blind Due to Medical Emergency

A subject's treatment assignment will not be broken until the end of the study for the clinical site study team unless medical treatment of the subject depends on knowing the study treatment the subject received. In the event that the blind needs to be broken because of a medical emergency, the investigator may unblind an individual subject's treatment allocation.

As soon as possible, the investigator should first contact the medical monitor to discuss the medical emergency and the reason for revealing the actual treatment received by that subject. The treatment assignment will be unblinded through interactive response technology. Reasons for treatment unblinding must be clearly explained and justified in the eCRF. The date on which the code was broken together with the identity of the person responsible must also be documented.

5.6 Treatment Compliance

The study vaccination will be administered to maintain the blind to site personnel conducting subject assessments. The location (in case of IM administration, right or left arm), date, and timing of all product administrations will be recorded in the subjects' eCRF. Compliance will be determined by the number and percentage of subjects who receive study vaccination. Any deviations from the dosing schedule outside the defined visit windows (Table 13-1) will be flagged in the clinical database.

5.7 Prior Vaccinations and Concomitant Therapy

Administration of medications, therapies, or vaccines will be recorded in the eCRF. Concomitant medications will include all medications (including vaccines) taken by the subject from the time of signing the ICF through 28 days after the boosting vaccination (or through the early termination visit if prior to that time). Intake will include whether there was knowledge of past pertussis vaccination and (when available) the year of receipt. Prescription and over-the-counter drugs will be included, as well as herbals, vitamins, and supplements. In addition, receipt of nonstudy vaccines will be solicited through approximately 28 days after the boosting vaccination and reported in the eCRF.

Use of new medication should prompt evaluation for the presence of a new diagnosis of chronic medical disease or condition. Medications that might interfere with the evaluation of the study vaccines should not be used during the study-reporting period unless clinically indicated as part of the subject's health care. New medications may indicate a new onset medical condition. As an example, the use of a bronchodilator medication due to wheezing (new prescription) will be used along with signs and symptoms to define a medically significant wheezing AE.

6 Study Assessments and Procedures

Before performing any study-related procedures, the investigator will explain the study to potential subjects and all potential subjects will be given an ICF to read and sign. Subjects will have the opportunity to have any questions answered before signing the ICF. The investigator must address all questions raised by the subject. The investigator or designee will also sign the ICF and a copy of the ICF will be given to the subjects. In addition, subjects will be asked to provide a signed informed consent for the use of samples for further pertussis-specific testing or assay development. The subjects will also be informed that a urine drug screen may be performed, at the discretion of the investigator, on any subject who experiences an AE. The schedule of events by study visit is shown in Table 13-1.

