NOTE: If a subject exceeds the screening window, they must be reconsented and screening must be reinitiated.

15. Use of corticosteroids in the respiratory tract (eg, nasal steroids, inhaled steroids) within 30 days prior to Day 1.
16. Receipt of a licensed vaccine within the last 30 days prior to Day 1 or planned vaccination during the active study conduct through Day 113. In the case of seasonal influenza, vaccination should not be withheld and is not contraindicated for subject participation. However, vaccination should be planned outside of a 30-day pre- and 30-day post-vaccination window whenever possible.
17. Known hypersensitivity to any component of the study vaccines.

18. Participation in any other clinical trial for the testing of an unlicensed product during the previous 6 months or planned during the study conduct.

NOTE: “Testing” is intended to mean receipt of an investigational product. Subjects in long term safety follow-up studies where vaccination has been completed greater than 6 months prior to this study enrollment are allowed.

19. Inability to adhere to the protocol, including plans to move from the area.
20. Personal history or family (first degree) history of congenital or hereditary immunodeficiency.
21. Past or present infection with human immunodeficiency virus, hepatitis B, or hepatitis C by screening test.
22. Any autoimmune or immunodeficiency disease/condition (inherited or iatrogenic).

NOTE: Stable endocrine disorders that have a confirmed autoimmune etiology (eg, thyroid, pancreatic) are allowed.

23. Any neurological disease or history of significant neurological disorder (eg, meningitis, seizures, multiple sclerosis, vasculitis, migraines*, Guillain-Barré syndrome [genetic/congenital or acquired]). *Significant neurological migraine includes frequent migraine (2 times a month or greater), migraine with aura or migraine with complications (status migrainosus, persist aura without infarction, infarction or aura triggered seizure defined by International Classification of Headache Disorders-3 [ICHD-3 2018]).
24. Any medical condition that, in the opinion of the investigator, might interfere with the evaluation of the study objectives or might affect the safety of the individual, eg, major depression or history of suicidal attempt.

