6.2.1 Concomitant Medication

Concomitant medications include all known medications (including herbal supplements, multivitamins and over-the-counter medications) taken by the subject from the time of signing the informed consent through 28 days after the boosting vaccination (or through early termination visit if prior to that time). Concomitant medications received associated with an SAE will be collected throughout the study period.

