The primary database lock will occur on Day 113 and all data collected through Day 113 will be included in the CSR and submitted to regulatory authorities. A subsequent longer-term safety follow-up, including longer-term persistence of immune responses, will occur through Day 254. These data will be provided in an addendum to the CSR. The clinical site study team directly participating in subject contact/care will remain blinded to the treatment assignment during this extended safety follow up period. All unblinded data analyses prior to primary database lock at Day 113 will be handled by the unblinded team of statisticians and programmers. A strict firewall between the blinded and unblinded teams will be maintained during study conduct.

This Phase 2b study is not designed to test a formal null hypothesis. Rather, it is intended to obtain preliminary assessment of the safety and immunogenicity induced by the BPZE1 lyophilized vaccine in healthy adults.

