7.7 Statistical Analysis Methodology

Statistical analysis will be performed using SAS software Version 9.3 or later. Continuous variables will be summarized using the mean, 2-sided 95% CI of the mean, SD, median, minimum value, and maximum value. Categorical variables will be summarized using

frequency counts and percentages, as well as 2-sided 95% CI for proportions computed using Clopper-Pearson method. Graphics of reverse cumulative distribution of anti-pertussis antibody titers will be generated for Days 29 and 113.

Where applicable, data analyses will be conducted for the prime period (prior to boosting) and boost period (at or post-boosting).

Data will be listed in data listings.

Further details of the planned statistical analyses, methods, and data conventions are described in the statistical analysis plan.

No formal hypothesis will be tested in this study.

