^c Inclusion/exclusion criteria and medical history will be reviewed and updated on Day 1 and Day 85 with specific vaccination exclusions applied.

^d Including date of birth (day, month, and year), sex, race, ethnicity, weight, height, and body mass index (derived).

^e Including prior and concomitant medical conditions, surgeries, and significant procedures.

^f Concomitant medications include all medications (including vaccines) taken by the subject from the time of signing the informed consent through 28 days after the boosting vaccination (or through early termination visit if prior to that time).

^g Only medications associated with serious adverse events.

^h Serology testing will include hepatitis B, hepatitis C, and human immunodeficiency virus.

- ⁱ Full physical examination at screening; symptom-directed (targeted) physical examination at all other scheduled time points. Interim physical examinations will be performed at the discretion of the investigator, if necessary. Height and weight will be measured at screening only.
- ^j On Day 1 (Visit 1) and 85 (Visit 5), targeted symptom-directed physical examination will be performed before vaccine administration.
- ^k On Day 1 (Visit 1) and 85 (Visit 5), vital sign measurements will be collected once before vaccine administration and at 60 minutes (± 15 minutes) after vaccine administration (before subjects are discharged).
- ^l Safety laboratory testing for safety cohort include (Table 13-2) hemoglobin, white blood count with differential, platelet count, sodium, potassium, random glucose, blood urea nitrogen, creatinine, calcium, albumin, total protein, bilirubin, alanine aminotransferase, aspartate aminotransferase, prothrombin time, and partial thromboplastin time. See Table 13-2 for specific laboratory tests to utilize for exclusion for the full cohort (kidney, hepatic, and hematology/coagulation only). Laboratory testing may be repeated once during the 30-day screening period if specific values used for exclusion criteria exceed toxicity Grade 1, with the last value being the value of record.
- ^m The first 48 subjects randomly assigned will be designated the safety lead-in cohort and safety laboratory testing will be performed in this subset beyond the screening visit. Should any laboratory value result in a grade 3 or greater toxicity score this lab must be entered as an adverse event and followed with retesting and observing for resolution or new clinical baseline

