4.3.2. Immunogenicity Analysis Set

The Immunogenicity Analysis Set will include all the Intent to Treat subjects who received the prime dose of the study vaccine(s) and have contributed both pre- and at least 1 post prime vaccination sample (mucosal or serum immunogenicity testing, respectively) for which valid results were reported and who have not received any component of a licensed pertussis vaccine in the 5 years through Day 113 of the study. Subjects will be classified according to the study vaccine received. For analysis of boosting, those subjects who have received all vaccinations and have a pre (Day 78 for mucosal and Day 85 for serum) and a post boost immune sample (Day 113) for which valid results were reported will be utilized. Additional testing for maximum response will be assessed for those subjects who received all vaccinations and have both a baseline sample (screening or Day 1 depending on the sample type) and a sample at Day 113. Immune persistence will be assessed in those subjects who contribute to sampling at Days 169 and 254.

Subjects will be classified according to the study vaccine received and according to humoral and mucosal immunity samples as described. Subjects who discontinued from study will be classified according to randomized treatment arm. Subjects who missed a boost dose, will be classified to no boost treatment arm based on prime arm. Subjects who received wrong vaccination by mistake and discontinued from study will be classified according to actual vaccination, priority higher.

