4.3.3. Per Protocol (PP) Analysis Set

The Per Protocol Analysis Set will include all subjects in the Immunogenicity Analysis Set, with the following exclusions:

- Data from all available visits for subjects following the receipt of unsuitable investigational product (either via dispensed/assigned or delivered).
- Data from all available visits for subjects found to be ineligible at baseline per Protocol Version 6.0.
- Data from all visits for subjects following the use of major immune-modulators, immune suppressants, receipt of blood products, or use of forbidden nasal solutions (eg, sprays, washes, neti pot) from 30 days prior to Day 1 through Day 113.
- Data from all visits for subjects following clinically significant protocol deviations that can affect the efficacy (immunogenicity) results.

- Data from any visit that occurs substantially out of window as defined by exceeding 30 days past the visit window or the time point whereby the follow-on visit should have occurred, whichever is most restrictive. Standard visit windows are described in schedule of events (Appendix 13.1).

For analyses using the Per Protocol Analysis Set, subjects will be grouped based on study vaccines actually received.

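### Outside pertussis vaccination after Day 113 is not solicited and triggers no exclusion, yet the Day 169, Day 254 and maximum-response endpoints would count the resulting titres

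*Protocol*

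**What the plan says.** **Recording.** Protocol 5.7 states that "receipt of nonstudy vaccines will be solicited through approximately 28 days after the boosting vaccination and reported in the eCRF". With the boost on Day 85 this is nominally Day 113. General concomitant medications have the same end point (Protocol 6.2.1, SAP 7.1.2). For the Day 169 and Day 254 visits, Table 13-1 footnote g narrows medication collection: "Only medications associated with serious adverse events".

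**Exclusion.** Eligibility criterion 16 (Protocol 4.1.2) bars "planned vaccination during the active study conduct through Day 113". The Immunogenicity Analysis Set (Protocol 7.5, SAP 4.3.2) leaves out anyone with a licensed pertussis vaccine in a five-year window that also closes at Day 113.

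**Use of the late samples.** Persistence to 9 months after the prime and 6 months after the two-dose series is a secondary objective (Protocol 2.2.1). SAP 4.3.2 adds no further condition on who contributes: "Immune persistence will be assessed in those subjects who contribute to sampling at Days 169 and 254". SAP 8.2.1 and 8.2.2 then compute seroconversion, geometric mean titre (GMT), geometric mean fold rise (GMFR), the maximum over pre-boost and the maximum during the study on the Immunogenicity Analysis Set, with Days 169 and 254 included.

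**The concern.** The plan treats an outside pertussis vaccine as disqualifying for immunogenicity, but applies that principle only up to the first database lock. A subject vaccinated elsewhere on, say, Day 140 breaks no stated rule, is not asked about it, and remains in every late analysis. The raised titre would be read as persistence of the study regimen or as its maximum response. Because the exposure is not solicited, the analyst could neither remove the sample at the second lock nor show that such cases were too few to matter.

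The event is plausible. Protocol 3.1.1 notes that acellular vaccines are given to adults as boosters, and the trial enrols adults who recall no pertussis vaccination in the past five years. The same section expects weaker responses to the acellular antigens from BPZE1 than from acellular vaccines. An outside dose might therefore move Arms A and B more than C and D; this is an inference, not something the documents quantify.

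**Working it through.** **1. The plan's own precision figures.** Protocol 7.7 specifies "2-sided 95% CI for proportions computed using Clopper-Pearson method". Recomputing the exact limits reproduces all 20 cells of Protocol Table 7-1 to rounding. For example, 50 of 100 gives 39.83 to 60.17 (stated 39.8, 60.2), and 25 of 50 gives 35.53 to 64.47 (stated 35.5, 64.5). The half-widths at a 50% rate are (60.2 − 39.8)/2 = 10.2 points for N = 100 and (64.5 − 35.5)/2 = 14.5 points for N = 50. They serve as the yardstick below.

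**2. The unobserved interval.** Solicitation ends nominally at Day 85 + 28 = 113. The gap is 169 − 113 = 56 days before the Day 169 sample and 254 − 113 = 141 days before the Day 254 sample (156 with the +15 window). As a share of the 253 days from Day 1 to Day 254, 141/253 = 56%.

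**3. Effect on fold rise.** The documents give neither an outside-vaccination rate nor a titre rise after such a dose, so both are assumptions. Let f be the share of an arm vaccinated elsewhere after Day 113 and R the fold rise. GMFR is the antilog of the mean log ratio (SAP 8.2.1). Multiplying a share f of the ratios by R adds f × ln R to that mean, so GMFR is multiplied by R^f. The same factor applies to GMT.

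**4. Effect on seroconversion.** If every such subject then seroconverts, and outside vaccination is unrelated to prior response, a true rate p rises by f × (1 − p).

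**5. Chance that an arm is touched at all.** P(at least one) = 1 − (1 − f)^N.

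| f | R^f, R = 4 | R = 10 | R = 20 | Added points, p = 30% | p = 50% | p = 70% | P(≥1), N = 50 | N = 100 |
|---|---|---|---|---|---|---|---|---|
| 1% | 1.014 | 1.023 | 1.030 | 0.7 | 0.5 | 0.3 | 40% | 63% |
| 2% | 1.028 | 1.047 | 1.062 | 1.4 | 1.0 | 0.6 | 64% | 87% |
| 5% | 1.072 | 1.122 | 1.162 | 3.5 | 2.5 | 1.5 | 92% | 99% |

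**6. Which endpoints take the effect.** The Day 254 sample carries all of it. Day 169 carries only vaccinations in the first 56 days. For the maximum endpoints R^f is an upper limit, because a late value counts only when it exceeds the subject's other values; any distortion from an outside dose is upward. Seroconversion on any day can be changed by one late sample. Seroconversion on all days also needs a positive result at the visits through Day 113, so an outside vaccine can alter it only for subjects already positive at each of those.

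**The case against.** The best defence is that the plan is not silent after Day 113. Protocol 6.2.1 says "Concomitant medications received associated with an SAE will be collected throughout the study period". Protocol 6.3.5.4 has subjects asked about new medications at every visit. Protocol 5.7 discourages interfering medications, the withdrawal reasons in 4.2.1 include disallowed substances, and the per-protocol exclusion for clinically significant deviations has no end date. A reader might infer that nothing at all is recorded or controlled after Day 113; these provisions show that this would be wrong. None of them captures a routine outside pertussis vaccine, however. The visit question does not name vaccines, the 5.7 advice has no defined period or analysis consequence, and vaccination after Day 113 is not a deviation from any stated rule.

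A reader might also extend the point to immunosuppressants and blood products, since the per-protocol rule on them runs "from 30 days prior to Day 1 through Day 113". The documents do not support that extension. The SAP's persistence tables use the Immunogenicity Analysis Set, which has no such exclusion at any time. SAP 8.3 names the per-protocol set only for sensitivity analysis of the primary endpoint, so moving its date would not change those tables. Nor would immunosuppression make a response look durable; it would tend to lower titres.

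The defence is right on two further matters. The protocol expects an acellular vaccine to generate less nasal immunity (1.2) and no measurable whole-cell response (3.1.1), so mucosal and whole-cell endpoints should be much less exposed. And because randomisation and continued blinding of site staff should make outside vaccination roughly similar across arms, the main exposure is in the absolute late estimates rather than the comparisons.

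**Conclusion.** The gap is real and follows from the text alone: solicitation and the set's own pertussis-vaccine exclusion both stop at Day 113, while endpoints on that set run to Day 254. Under assumed outside vaccination of 1–5% and a 4- to 20-fold rise, an affected arm's late serum GMFR is inflated by about 1–16%. Seroconversion rises by about 0.5–2.5 points at a true rate of 50%, which is small against half-widths of 10.2 and 14.5 points. It would be tempting to conclude that outside boosting will in fact be reported as durable response, or that the distortion is large. Neither follows, because the documents give no basis for the rate or the fold rise. What they do show is that the plan could not detect the problem if it arose.

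The stakes are limited. The primary endpoint (Days 29 and 113) and the Day 113 clinical study report are untouched; the late data go into an addendum. As the opening of Protocol Section 7 says, "This Phase 2b study is not designed to test a formal null hypothesis", so no test is at risk. This is an inexpensive improvement to secondary persistence results.

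**What to change.** **Collection (Protocol 5.7, 6.2.1, Table 13-1 footnote g and the eCRF).** At the existing Day 169 and Day 254 visits, ask about and record any non-study pertussis-containing vaccine, with its date. Record systemic immunosuppressants, immunoglobulin and blood products as well, for description only. This changes what is recorded, not what subjects may receive.

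**Analysis (Protocol 7.5, SAP 4.3.2).** For Day 169, Day 254 and the maximum endpoints, let the pertussis-vaccine exclusion run to the date of the sample instead of Day 113, and drop only samples taken after the outside vaccine. Word it as a non-study vaccine, since Boostrix is itself a licensed pertussis vaccine. Report late serum PT, FHA and PRN results with and without the dropped samples.

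**Cost.** A short protocol and eCRF amendment, a brief set of questions at two visits that already take place, a changed end date in the SAP, and the loss of a few late samples.
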